9.2. Adverse Events

Verbatim terms on the OLE Adverse Event eCRFs will be mapped to PT and SOC using MedDRA version 19.0. AEs will be reported and severity will be categorized using the Common Terminology Criteria for Adverse Events (CTCAE, Version 4.03).

AE summaries will use the OLE Safety Population.

All AE summaries will be restricted to treatment-emergent adverse events (TEAEs), which are defined as any AE that newly appears, increases in frequency, or worsens in severity following initiation of study drug and up to 30 days after date of last dose or last study visit, whichever is later. If it cannot be determined whether the AE is treatment emergent due to a partial onset date, then it will be counted as such.

Each AE summary will be displayed by treatment group. Summaries that are displayed by SOC and PT will be ordered by descending order of NEOD001-OLE001 24 mg/kg incidence of SOC and PT within each SOC.

The following listings will be presented by subject, with non-TEAEs flagged:

- All AEs
- Serious adverse events (SAEs) (this is a subset of the AEs where serious is marked as “Yes”)
- CTCAE Grade 3 or higher AEs (this is a subset of AEs where severity is missing or marked as CTCAE Grade 3, 4, or 5)
- Related AEs (this is a subset of the AEs where relationship marked as “Related” or relationship is missing)
- AEs leading to Study Drug Withdrawal (this is a subset of the AEs where Action Taken with Study Treatment is checked as “Drug Discontinued”)
- Fatal AEs (this is a subset of the AEs where outcome is indicated as “Fatal” or the CTCAE grade is 5)
- AEs resulting in any dose change (i.e., interruption, reduction, held, or prolongation)
- AEs assessed by the investigator as infusion-associated (this is a subset of the AEs where infusion-associated AE was reported as "Yes.")
- AEs within one day of any infusion (this is a subset of the AEs where AE onset date was the same day as the date of any infusion)

9.2.1. Types of Incidence Rates

9.2.1.1. Crude Incidence Rates

The crude rate for a particular AE is defined as the number of subjects with the AE divided by the number of subjects exposed to the study drug. All crude incidence tables will be repeated only for MedDRA PT, excluding MedDRA SOC.

To assess the long-term treatment effects overall and relative to shorter term treatment, the crude incidence of TEAEs will be summarized by combined study from the original parent study and OLE study (NEOD001-001), followed by the OLE only (NEOD001-OLE001). TEAEs that started in the original parent study will be summarized for subjects who initiated at 24 mg/kg, subjects who ever took 24 mg/kg, and subjects who took any dose of NEOD001. TEAEs that start on or after the first dose of OLE NEOD001 (i.e., OLE TEAEs) will be summarized using the OLE dose 24 mg/kg. The treatment group schema is shown in [Table 6](#) using the NEOD001 Safety Population.

Table 6: Treatment Group Schema

NEOD001-001 + NEOD001-OLE001			NEOD001-OLE001
Initiated at 24 mg/kg (N=xx)	All 24 mg/kg (N=xx)	Any Dose (N=xx)	24 mg/kg (N=xx)

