7. STUDY POPULATION

7.1. Subject Disposition

Subject disposition will be tabulated for all screened subjects and will include:

- the number of subjects dosed in the original parent study (NEOD001-001; NEOD001 Safety Population)
- the number of subjects screened in the OLE
- the number screened but not enrolled in the OLE
- the number enrolled in the OLE (OLE Safety Population)
- the number in each analysis organ evaluable population
- the number who discontinued treatment early in the OLE and reason(s) for discontinuation of treatment as recorded on the OLE eCRF
- the number who withdraw from OLE study prior to completing the study and reason(s) for withdrawal as recorded on the OLE eCRF

Time on study will be calculated as last known date of contact minus date of first infusion in NEOD001-OLE001 plus one.

By-subject data listings of all the above study disposition data including study completion and any reasons for premature treatment and/or study withdrawal will be presented.

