9. SAFETY ANALYSES

Safety analyses will be conducted using the NEOD001 and OLE Safety Populations as specified below.

No inferential comparison of safety endpoints will be performed, unless otherwise specified.

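### SAP 9.2.1.1 and Table 6 disagree on which events the combined columns hold, set no onset rule for the All 24 mg/kg column, and conflict with 9.2 on the population; 9.2.2 cites the wrong table

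*SAP*

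**What the plan says.** SAP 9.2.1.1 defines the crude rate as "the number of subjects with the AE divided by the number of subjects exposed to the study drug". It states the purpose as follows: "To assess the long-term treatment effects overall and relative to shorter term treatment, the crude incidence of TEAEs will be summarized by combined study", meaning the parent study and the OLE together, followed by the OLE alone. Table 6 places three columns (*Initiated at 24 mg/kg*, *All 24 mg/kg*, *Any Dose*) under the heading "NEOD001-001 + NEOD001-OLE001" and a fourth under the OLE alone.

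The sentence that describes the first three groups reads "TEAEs that started in the original parent study will be summarized for subjects who initiated at 24 mg/kg, subjects who ever took 24 mg/kg", and then adds subjects on any dose. Events that begin on or after the first OLE dose go to the OLE 24 mg/kg group. The schema is drawn up "using the NEOD001 Safety Population", which SAP 5 defines as everyone dosed in the parent study.

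Section 9 opens with "Safety analyses will be conducted using the NEOD001 and OLE Safety Populations as specified below". Section 9.2 then says "AE summaries will use the OLE Safety Population", with no exception. Section 9.2.2 lays out the overall crude summary according to Table 7, which 9.2.1.2 uses to illustrate the life-table method.

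**The concern.** Two programmers could fill the same three columns differently and each point to a sentence in the SAP. One would count events from both studies; the other would count parent-onset events only, under a heading that says both. A reader of the report could not tell which was done.

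The *All 24 mg/kg* column raises a separate question. Membership depends on having ever received 24 mg/kg, and nothing ties the event to that dose. A subject who began lower and moved up carries the earlier events into a column labelled 24 mg/kg.

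Frequency and severity of adverse events are primary endpoints (SAP 2.3.1). SAP 8 and 11 drop all efficacy tables and figures, so the safety tables carry most of the summarized results.

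**Working it through.** **1. Table 7, the only computed figure in this part of the SAP.** At risk = (entering + (entering − lost))/2; P = SAEs/at risk; cumulative incidence = 1 − product of (1 − P).
- Second interval: (1800 + 1401)/2 = 1600.5; P = 1/1600.5 = 0.0006.
- All 12 rows reproduce. The 12-month value is 0.05499, stated as 0.055.
- SAEs: 0+1+0+2+0+5+8+9+2+0+1+2 = 30; crude rate 30/3000 = 0.01, as stated.

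The table is a correct worked example on 3000 hypothetical subjects. It has no treatment columns, so it cannot be the layout for the 9.2.2 summary. Table 6 is the treatment-group schema.

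**2. Event scope of the combined columns.** The two rules side by side:
- Lead sentence and Table 6 heading: parent plus OLE.
- Group-defining sentence: parent-onset events only, with OLE-onset events sent to the fourth column.

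Both cannot govern the same three columns. For illustration, take N = 27 + 42 = 69 parent subjects (Protocol 1.3.2) and assume that 5 had the event with parent onset and b others had first onset in the OLE. *Any Dose* then reads 5/69 or (5 + b)/69:

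| b (assumed) | Group-defining sentence | Table 6 heading |
|---|---|---|
| 0 | 7.2% | 7.2% |
| 5 | 7.2% | 14.5% |
| 10 | 7.2% | 21.7% |
| 15 | 7.2% | 29.0% |

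**3. Lower-dose events.** Parent doses ran from 0.5 to 24 mg/kg (Protocol 1.3.2), and the planned OLE dose is 24 mg/kg (Protocol 1.4). Under the combined heading, a lower-dose parent subject who enters the OLE joins *All 24 mg/kg* together with earlier events. Having both an *Initiated* and an *All* column implies that some such subjects are expected, but their number is not given. Per 10 such subjects with m months below 24 mg/kg and an assumed constant event rate h per month, at most 10 × (1 − exp(−h × m)) are counted for a lower-dose event:
- h = 2%: m = 3 gives 0.58; m = 6 gives 1.13.
- Range: 0.30 (h = 1%, m = 3) to 2.13 (h = 4%, m = 6).

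*Initiated at 24 mg/kg* is not affected.

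**4. Population.** Take 10 subjects with an OLE-onset event. Over all 69 parent subjects the OLE column reads 10/69 = 14.5%. Over an assumed 60, 50, 40 or 30 OLE entrants it reads 16.7%, 20.0%, 25.0% or 33.3%. Conversely, applying the 9.2 sentence to the combined columns removes any parent subject who did not enter the OLE.

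**5. Follow-up.** This bears only on the optional additions.
- Parent mean: 994/69 = 14.41 infusions; ((14.41 − 1) × 28 + 30)/30.4375 = 13.3 months.
- OLE ceiling: (35 × 28 + 30)/30.4375 = 33.2 months.
- At an assumed 2% per month, 1 − exp(−h × t) gives 23.4% and 48.5% (1%: 12.5% and 28.2%; 4%: 41.3% and 73.5%).

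This sets a mean against a maximum that program discontinuation (SAP 11) makes unlikely for many subjects, so it shows direction rather than expected size.

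**The case against.** The strongest reply is that most of this can be settled by reading the SAP sensibly.

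- **Denominators.** A reader might infer that no stated population can serve all four columns. The documents do not support that. OLE subjects must have had at least 9 months of parent-study treatment (Protocol 4.1), so they are a subset of the NEOD001 Safety Population. The subjects-exposed definition and the separate N per column then largely fix each denominator. What stands is that the 9.2 sentence admits no exception and so conflicts with 9.2.1.1 as written.
- **OLE results.** A reader might infer that the OLE safety findings themselves are compromised. They are not. The OLE column is defined by onset on or after the first OLE dose, SOC/PT tables are ordered by OLE incidence, and all events appear in by-subject listings.
- **Follow-up.** A reader might infer that unequal follow-up is ignored. SAP 9.2.1.2 explains why crude rates mislead and plans life tables from the first parent dose; 9.2.3 to 9.2.9 apply cumulative incidence to most event categories. What remains is that the life tables cover OLE entrants only and are not split by the Table 6 dose columns.
- **Dose grouping.** Grouping by ever having taken 24 mg/kg is a clear subject-level rule. It is nevertheless silent on onset, and the column label suggests events at that dose.

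The analyses are descriptive, so no error rate is involved.

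**Conclusion.** Four textual defects stand without any calculation: the contradictory event scope of the combined columns, the missing onset rule for *All 24 mg/kg*, the population conflict between 9.2 and 9.2.1.1, and the Table 7 citation in 9.2.2. The first matters most, because literal programming leaves OLE-onset events out of columns labelled as combined.

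The documents do not allow the effect to be sized. OLE entry numbers, event counts, the number of subjects who moved up to 24 mg/kg and their time at lower doses are not given, so every percentage above is an illustration. In particular, nothing supports a claim that lower-dose events make up a large share of the 24 mg/kg column. The SAP should be corrected before the tables are programmed. The need for extra exposure-adjusted displays is a matter of preference.

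**What to change.** - **(a)** Reword 9.2.1.1 so that the three combined columns include both parent-onset and OLE-onset TEAEs.
- **(b)** For *All 24 mg/kg*, count only TEAEs with onset on or after the subject's first infusion at the assigned (planned) 24 mg/kg level. Use the planned dose level per visit in SAP 9.1, not actual mg/kg. Under the 2500 mg cap actual mg/kg falls below 24 in heavier subjects (at 120 kg, 2500/120 = 20.8 mg/kg), and in the parent study it is derived only where both dose and weight are available.
- **(c)** In 9.2, add an exception for summaries where another population is specified. State the denominators: NEOD001 Safety Population restricted to the dose group for the combined columns, and OLE Safety Population for the OLE column.
- **(d)** In 9.2.2, replace Table 7 with Table 6.

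Optional: add a parent-onset column and descriptive exposure-adjusted incidence for each period, noting that OLE entrants are selected for at least 9 months of prior treatment.

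The cost is SAP wording and a little programming on data already held. The optional items make the tables slightly longer.

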9.2.1.2. Cumulative Incidence Rates

The cumulative incidence rate is the probability that a particular AE occurs by a specified time. To compute the cumulative rate using the life table method, exposure time intervals from the first NEOD001 dose of the original parent study (NEOD001-001) (i.e., ≤1 month, >1 month to ≤3 months, >3 month to ≤6 months, >6 months to ≤1 year, >1 to ≤1.5 years, >1.5 to ≤2 years, >2 to ≤3 years, ..., and > maximum years) are specified, and the number of subjects at risk of experiencing an AE in each time interval is determined by taking the average number of subjects at risk at the start and end of each time interval. As subjects leave the study over time, the number of subjects at risk of experiencing the AE in each time interval decreases. The cumulative incidence rate over each time intervals is as follows:

$$1 - \{[1 - P(t_1)][1 - P(t_2)] \dots [1 - P(t_k)]\}$$

where $P(t_i)$ is the number of subjects with the AE divided by the number of subjects at risk in time interval t_i and where i ranges from 1 to k .

To illustrate the difference between crude and cumulative incidence rates and how these are computed, an example is provided (O'Neill, 1988). Suppose that 3000 subjects are initially exposed to a drug and followed for up to 1 year with varying durations of exposure (see Table 7). Assume further that 30 subjects experience SAEs, most of which occur later in the study as duration of exposure increases. The crude rate is $30/3000 = 0.01$ and the 12-month cumulative rate is 0.055. When AEs occur later in time as fewer subjects are at risk due to discontinuations or tolerability, the crude rate underestimates the longer-term risk and overestimates the shorter-term risk.

Using the example in Table 7, the number of subjects at the start of a time interval is the number of subjects at the start of the previous time interval minus the number of subjects lost to follow-up or who dropped out minus the number of subjects with SAEs. For instance, the number of subjects at the start of the 3rd time interval is equal to

$$[1800 - 399 - 1] = 1400$$

The proportion of subjects with SAEs at each time interval $P(t_i)$ is computed by dividing the number of subjects with SAEs by the number of subjects at risk in the time interval. For example, the number of subjects at risk for the 2nd time interval is as follows:

$$\frac{[1800 + (1800 - 399)]}{2} = 1600.5$$

The proportion of subjects with SAEs in the 2nd time interval, $P(t_2)$ is therefore $1/1600.5$ or 0.0006. The 12-month cumulative SAE incidence rate is

$$P(t) = 1 - [(1 - 0.0000) \times (1 - 0.0006) \times (1 - 0.000) \times (1 - 0.0021) \times \dots \times (1 - 0.0100)] = 0.055$$

which is 1 minus the cumulative probability of not having any SAE up to the 12th time interval.

Table 7: Example of Computing Cumulative Incidence Rates Using the Life Table Method

Interval (months)	Number Entering Interval	Number Lost to Follow-Up	Number with SAE	Number at Risk	Proportion with SAE	Cumulative Incidence Rate
0–1	3000	1200	0	2400	0.0000	0.0000
1–2	1800	399	1	1600.5	0.0006	0.0006
2–3	1400	400	0	1200	0.0000	0.0006
3–4	1000	98	2	951	0.0021	0.0027
4–5	900	100	0	850	0.0000	0.0027
5–6	800	95	5	752.5	0.0066	0.0094
6–7	700	92	8	654	0.0122	0.0215
7–8	600	91	9	554.5	0.0162	0.0374
8–9	500	98	2	451	0.0044	0.0416
9–10	400	100	0	350	0.0000	0.0416
10–11	300	99	1	250.5	0.0040	0.0454
11–12	200	0	2	200	0.0100	0.0550

Source: O'Neill, 1988.

Summaries of cumulative incidence rates will be presented for the OLE Safety Population, based on TEAEs experienced from the start of the original parent study (NEOD001-001). Cumulative incidence rates will be computed separately for each MedDRA SOC and each MedDRA PT within SOC.

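### The life-table AE cumulative incidence in SAP 9.2.1.2 has no place for death as a competing event, so it estimates risk in the absence of death rather than the probability the SAP defines

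*SAP*

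**What the plan says.** SAP 9.2.1.2 gives the target as a probability: "The cumulative incidence rate is the probability that a particular AE occurs by a specified time". The estimator is 1 − {[1 − P(t1)] … [1 − P(tk)]}, where P(ti) is events divided by subjects at risk in interval ti. The number at risk comes from "taking the average number of subjects at risk at the start and end of each time interval".

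Two exits from the risk set are described. The number entering an interval is the previous entering number "minus the number of subjects lost to follow-up or who dropped out minus the number of subjects with SAEs". On attrition generally, the SAP says: "As subjects leave the study over time, the number of subjects at risk of experiencing the AE in each time interval decreases". After the worked example it describes the result as the quantity "which is 1 minus the cumulative probability of not having any SAE up to the 12th time interval".

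The rates are for the OLE Safety Population, timed from the first parent-study dose, and "Cumulative incidence rates will be computed separately for each MedDRA SOC and each MedDRA PT within SOC". Neither the section nor Table 7 mentions death or competing events. SAP 8.2 and protocol 8.7 say only that missing data are not imputed.

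**The concern.** A subject who has died cannot later have the AE. A product of interval-specific non-event probabilities that drops such a subject as a withdrawal implicitly gives him or her the same future AE risk as those still followed. That answers a different question: how often the AE would occur if nobody could die first. The answer is never below the stated probability. It is above it once deaths without the AE have removed subjects who are then assumed to remain at risk.

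The plan itself expects deaths. Overall survival is an exploratory objective, and SAP 9.2.7 schedules a cumulative incidence of deaths. Protocol 7.4.3 keeps death due to disease progression, as such, out of AE and SAE reporting. Because rates are computed per SOC and per preferred term, most deaths are not the event being counted in any given row.

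Long-term safety is the primary objective, and the cumulative rates recur through SAP 9.2.3 to 9.2.9. A reader will take them as the probabilities that the SAP says they are.

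**Working it through.** **The SAP's own figure.** The example starts from 3000 subjects with 30 SAEs. With number at risk = entering − lost/2, interval 2 gives 1800 − 399/2 = 1600.5 and P = 1/1600.5 = 0.0006. All 12 rows of Table 7 reproduce to four decimals, and the product gives 0.0550 (0.0548 if the rounded proportions are multiplied). This agrees with the text that "the 12-month cumulative rate is 0.055"; the crude rate is 30/3000 = 0.01. The arithmetic is right. The issue is what is being estimated.

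**How the same table behaves if some of the lost subjects had died.** This uses the multiple-decrement life table: r = entering − censored/2; F increases by S × events/r; S is multiplied by 1 − (events + deaths)/r. The share of the lost column that is deaths is an assumption, for illustration only.

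| Share of lost that are deaths | 12-month incidence |
|---|---|
| 0% | 0.0550 |
| 5% | 0.0503 |
| 10% | 0.0460 |
| 25% | 0.0354 |
| 50% | 0.0230 |
| 100% | 0.0100 (the crude rate) |

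**This study's setting.** Inputs from the documents:
- The clock starts at the first parent-study dose (SAP 9.2.1.2).
- Entry requires at least 9 months of parent-study treatment (protocol 4.1), so nobody in the OLE Safety Population can die in the first t0 = 0.75 years.
- Treatment in the extension lasts up to 36 months (protocol 3.5).
- The TEAE window closes 30 days after last dose or at the last study visit, whichever is later (SAP 9.2), so only deaths inside it compete.

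Assumptions: constant AE hazard a, constant death hazard d after t0, horizon t = 3.5 years.

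- SAP method: 1 − exp(−a·t).
- Stated probability: 1 − exp(−a·t0) + exp(−a·t0) × [a/(a+d)] × {1 − exp[−(a+d)(t − t0)]}.

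For a = 0.2 and d = 0.10 per year, the SAP method gives 1 − exp(−0.7) = 50.34%. The stated probability is 0.1393 + 0.8607 × 0.6667 × (1 − 0.4382) = 46.16%. The excess is 4.18 points.

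| Assumed death hazard per year | a = 0.2: SAP method 50.34% | Excess, points | a = 0.1: SAP method 29.53% | Excess, points |
|---|---|---|---|---|
| 0.02 | 49.45% | 0.89 | 28.96% | 0.57 |
| 0.05 | 48.16% | 2.18 | 28.13% | 1.40 |
| 0.10 | 46.16% | 4.18 | 26.85% | 2.68 |
| 0.20 | 42.64% | 7.70 | 24.60% | 4.93 |

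**Sensitivity to the horizon.** At 48 months with the same 9-month lead-in, take an AE that the SAP method shows as 30%. Its probability is 29.3%, 28.2%, 26.6% or 23.5% when the assumed yearly probability of death is 2%, 5%, 10% or 20%. Running the SAP's grouped intervals on expected counts gives nearly the same answers (for example 29.99% against 26.56% at 10%), so grouping is not the source of the gap.

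**The case against.** The strongest reply is that the effect may be negligible here. No death rate is given for these subjects. The mortality figures in protocol 1.2 are the cardiac share of deaths and transplant-related mortality, and protocol 5.6.2 prohibits myeloablative chemotherapy with transplant. Participants have already completed at least 9 months of treatment and meet performance-status and organ-function criteria, and deaths found later by telephone follow-up fall outside the TEAE window. At 0.02–0.05 per year the excess is about 0.6 to 2.2 points. The 95% half-width for a simple proportion of 30% or 50% is 1.96 × √(0.3 × 0.7/69) = 10.8 or 1.96 × √(0.5 × 0.5/69) = 11.8 points, taking the parent study's 69 subjects as a ceiling. All of this stands and limits the importance of the point. It does not remove the mismatch: sampling error is not systematic, whereas this error always runs upward.

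It is also fair that the SAP never says that deaths are censored. That follows from a formula with two exits and no competing-event term, and no other section corrects it.

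A reader might infer more than the documents support:
- *A larger excess.* Applying the death hazard from day 0 gives 3.7, 7.0 and 12.7 points for a = 0.2 at 0.05, 0.10 and 0.20 per year. That ignores the death-free entry period; the figures become 2.2, 4.2 and 7.7.
- *That rates for different AEs could add to an impossible total.* AEs are not mutually exclusive, so their incidences may properly sum to more than 100% under any estimator.
- *That these are the main long-term AE estimates.* SAP 9.2.1.1 gives the comparison of long-term with shorter-term treatment to the crude incidence, and the overall summary in SAP 9.2.2 is also crude.
- *That the wide intervals are an error.* Grouping belongs to the life-table method, and some dates are imputed under SAP 4.3.

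**Conclusion.** The point holds as a mismatch between the stated quantity and its estimator. The direction is certain: the SAP method is at or above the probability it defines. The size cannot be settled from the documents. Under the constant-hazard assumptions above it is small at mortality of 5% per year or less, and material at 10–20% per year (about 2.7 to 7.7 points across the two AE hazards).

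The scope is limited. The cumulative incidence of deaths is unaffected because death is the event there. A fatal AE counts as an event under its own term. Crude rates do not use the formula. SAP 9 plans no inferential safety comparison unless otherwise specified, and no hypothesis test depends on these rates. The change is worth making because the output bears on the primary objective and would otherwise carry a description that it does not meet.

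**What to change.** In SAP 9.2.1.2, state how a death without the AE is handled. For the non-fatal AE summaries, estimate cumulative incidence with the Aalen-Johansen estimator, or with the equivalent multiple-decrement life table on the SAP's existing intervals. Treat death without the AE within the TEAE window as a competing event, and other exits as censoring. If the present life table is kept as a secondary display, label it as risk in the hypothetical absence of death, and do not describe it as the probability that the AE occurs.

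The inputs are already planned: AE onset dates are collected (protocol 7.1), and SAP 4.3 has rules for partial onset and death dates. The cost is slightly more output and less comparability with life-table displays from other studies.

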1.3.2 Clinical Safety

The safety and tolerability of NEOD001 have been investigated in the Phase 1/2 study (Study NEOD001-001) in the US, and are being investigated in the following ongoing global studies:

- Phase 1/2 open-label extension study (Study NEOD001-OLE001)
- Phase 2b study (Study NEOD001-201)
- Phase 3 study (Study NEOD001-CL002)

Study NEOD001-001 was a Phase 1/2 open-label, dose escalation study of the IV administration of single-agent NEOD001 in subjects with AL amyloidosis, which enrolled 27 subjects in the Escalation Phase in 7 cohorts (evaluating dose levels from 0.5 mg/kg to 24.0 mg/kg) and enrolled an additional 42 subjects in the Expansion Phase. The most frequently reported treatment-emergent adverse events (TEAEs) overall in Study NEOD001-001 (occurring in $\geq 10\%$ of subjects [N=69], regardless of relationship to NEOD001) were fatigue, nausea, upper respiratory tract infection, diarrhea, anemia, blood creatinine increased, dizziness, constipation, cough, headache, edema peripheral, vomiting, pain in extremity, back pain, dyspnea, edema, muscle spasms, rash, and urinary tract infection (Gertz et al, 2016). No confirmed anti-NEOD001 antibodies were detected. No dose-limiting toxicities (DLTs) or related serious adverse events (SAEs) were reported.

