4 SELECTION, DISCONTINUATION, AND WITHDRAWAL OF SUBJECTS

4.1 INCLUSION CRITERIA

Subject must meet *all* of the following:

1. Previously enrolled and treated for at least 9 months in Study NEOD001-001
2. Ability to understand and willingness to sign an informed consent form (ICF) prior to initiation of any study procedures
3. Has adequate bone marrow reserve, hepatic and renal function, as demonstrated by:
 - Absolute neutrophil count (ANC) $\geq 1.0 \times 10^9/L$
 - Platelet count $\geq 75 \times 10^9/L$
 - Hemoglobin ≥ 9 g/dL
 - Total bilirubin ≤ 2 times the upper limit of normal (\times ULN)
 - Aspartate aminotransferase (AST) and/or alanine aminotransferase (ALT) $\leq 3 \times$ ULN
 - Estimated glomerular filtration rate ≥ 30 mL/minute
4. Seated systolic blood pressure (BP) 90 to 180 mmHg
5. ECOG PS 0 to 2
6. Women of childbearing potential (WOCBP) must have a negative serum pregnancy test within 28 days prior to the first administration of study drug and agree to use highly effective physician-approved contraception ([Appendix 1](#)) from 30 days prior to the first study drug administration to 90 days following the last study drug administration
7. Male subjects must be surgically sterile or must agree to use highly effective physician-approved contraception ([Appendix 1](#)) from 30 days prior to the first study drug administration to 90 days following the last study drug administration

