5. ANALYSIS POPULATIONS

The NEOD001 Safety Population will include all subjects who received any amount of NEOD001 in the original parent study (NEOD001-001).

The OLE Safety Population will include all subjects who received any amount of NEOD001 in the OLE study.

The Cardiac Evaluable Population will include subjects who had cardiac involvement in the original parent study (NEOD001-001), defined as subjects who had an NT-proBNP \geq 650 ng/L at Screening and at least one post-baseline assessment of NT-proBNP.

The Renal Evaluable Population will include subjects who had renal involvement in the original parent study (NEOD001-001), defined as proteinuria $>0.5\text{g/day}$ in a 24-hour urine collection (the value reported as Total Protein on the Disease Specific Urine Laboratory Tests CRF) at Screening and at least one post-baseline assessment of proteinuria.

The Peripheral Neuropathy Evaluable Population will include subjects who had peripheral nerve involvement in the original parent study (NEOD001-001), defined as subjects who were marked as having had peripheral nerve involvement at baseline per the Amyloidosis Baseline Disease Assessment AND had a Screening peripheral neuropathy assessment score of 2 or greater from the Peripheral Neuropathy Assessment CRF and at least one post-baseline peripheral neuropathy assessment from the Peripheral Neuropathy Assessment CRF.

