9.2.7. Serious Adverse Events and Deaths

The crude incidences of serious TEAEs will be summarized. The incidence of fatal TEAEs will be summarized separately. In addition, the cumulative incidences of serious TEAEs and deaths will be summarized. The following summaries will be presented:

- Subject incidence of serious TEAEs by MedDRA SOC and PT
- Subject incidence of serious related TEAEs by MedDRA SOC and PT
- Subject incidence of fatal TEAEs by MedDRA SOC and PT

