9.2.8. Adverse Events Leading to Study Drug Withdrawal

AEs leading to study drug withdrawal are those AEs where Action Taken with Study Treatment is checked as “Drug Discontinued”. The crude and cumulative incidences of AEs leading to study drug withdrawal will be summarized. The following summaries will be presented:

- Subject incidence of TEAEs leading to study drug withdrawal by MedDRA SOC and PT

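### Cumulative AE incidence is timed from the first parent-study dose but computed only in subjects who reached the OLE, so deaths by death date and permanent drug stops by stop date cannot appear in the first 6 months

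*SAP*

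**What the plan says.** SAP Section 9.2.1.2 defines the quantity: "The cumulative incidence rate is the probability that a particular AE occurs by a specified time". The life table uses "exposure time intervals from the first NEOD001 dose of the original parent study", cut at 1, 3, 6 and 12 months and then at wider steps. The rates are "presented for the OLE Safety Population, based on TEAEs experienced from the start of the original parent study".

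SAP Section 5 fixes that cohort: "The OLE Safety Population will include all subjects who received any amount of NEOD001 in the OLE study". Protocol Section 4.1, criterion 1, sets the entry condition: "Previously enrolled and treated for at least 9 months in Study NEOD001-001".

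Two planned outputs are directly affected. Under SAP Section 9.2.7, "the cumulative incidences of serious TEAEs and deaths will be summarized". Under Section 9.2.8, "The crude and cumulative incidences of AEs leading to study drug withdrawal will be summarized".

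On the population for AE tables in general, Section 9.2 names the OLE Safety Population. Section 9.2.1.1 says the crude-rate schema (Table 6) uses the NEOD001 Safety Population, which is everyone dosed in the parent study. The opening of Section 9 allows both populations, as specified in each subsection.

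**The concern.** The clock and the cohort do not match. A subject can be in the cohort only by having survived and stayed on treatment long enough to enter the OLE, but the life table credits that subject with risk time from the first parent dose. For death and permanent drug stop, that early time is immortal: no event could have happened in it to anyone who is counted.

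Long-term safety is the primary objective, and Section 9.2.1.2 adds cumulative rates precisely because crude rates misstate risk when subjects drop out over time. As planned, the early rates for these two event classes are not the probability that the section defines. A reader could take a zero at 6 months as evidence of safety when it only reflects who was allowed into the table.

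**Working it through.** **1. The plan's own example.** Table 7 uses number at risk = number entering − (number lost)/2, P(t) = events / number at risk, and cumulative rate = 1 − Π[1 − P(t)].

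- Second interval: 1800 − 399/2 = 1600.5 at risk; 1/1600.5 = 0.0006.
- All 12 rows reproduce. The 12-month result is 0.05499 against the stated 0.055, and the crude rate is 30/3000 = 0.01.

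The arithmetic is sound. In the example everyone enters at time 0 and subjects only leave; there is no provision for late entry.

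**2. How early could a subject qualify for the OLE?** SAP Section 4.5 sets 1 month = 30.4375 days, so 6 months = 6 × 30.4375 = 182.6 days. The protocol does not define 9 months, so several readings are tried:

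| Reading of 9 months | Days | Months |
|---|---|---|
| Calendar months: 9 × 30.4375 | 273.9 | 9.00 |
| 28-day months: 9 × 28 | 252 | 8.28 |
| Nine infusions, 28 days apart: 8 × 28 + 1 | 225 | 7.39 |
| Nine infusions, each interval 5 days short: 8 × 23 + 1 | 185 | 6.08 |

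The spacing and 5-day window in the last two rows are the OLE's; applying them to the parent study is an assumption. Every reading exceeds 182.6 days.

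**3. Consequence for the early intervals.** A subject who died, or stopped NEOD001 for good, by month 6 cannot have met criterion 1 and is not in the cohort. Placed by death date or stop date, these events number zero in the intervals up to 1, 3 and 6 months. In the 6-to-12-month interval, OLE subjects count in the denominator for time in which they could not have had the event.

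**4. Size in the early intervals.** Protocol Section 1.3.2 gives 69 subjects dosed in the parent study. With x omitted events by month 6 and no other dropout, the all-subject value is x/69 and the planned table shows 0:

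- x = 1: 1/69 = 1.4%
- x = 3: 3/69 = 4.3%
- x = 5: 5/69 = 7.2%

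These x values are assumptions. The documents give no parent-study counts of deaths, withdrawals or roll-overs. If x = 0, nothing is lost in these intervals.

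**5. Later intervals: direction not fixed.** Two hypothetical cases at month 18, with everyone else followed event-free beyond month 18 so that the life table reduces to a proportion:

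- Five of 69 die by month 6, the other 64 enter the OLE, and 8 of these die by month 18. OLE only: 8/64 = 12.5%. All parent subjects: 13/69 = 18.8%. The planned figure is too low.
- Forty of 69 enter at month 10 and 8 of them die in months 11 to 18. Of the 29 who do not enter, 1 dies at month 5. OLE only: 8/40 = 20.0%. All parent subjects: 9/69 = 13.0%. The planned figure is too high, despite the omitted death.

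**The case against.** **The dating rule.** The SAP never says whether a fatal or treatment-ending TEAE is placed by onset or by outcome. Elsewhere it works from start dates (Sections 9.2.1.1 and 9.2.9), and Section 9.2.8 identifies withdrawal events by the action-taken box with no separate date. Under onset dating, an AE that began before month 6 and later proved fatal or ended treatment in the OLE would sit in an early interval. This stands, so the guaranteed zero is limited to death dates and stop dates. It does not repair the cohort: events in parent subjects who never reached the OLE are missing under either rule.

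**Parent-study events appear elsewhere.** If Section 9.2.1.1 is a specific exception to Section 9.2, the combined crude columns still count parent-study deaths and withdrawals. That is a fair reading, but crude rates carry no timing.

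**The cohort is disclosed and defensible.** The section names the OLE Safety Population, and describing subjects treated for 9 months or more suits an extension study. That supports a clock starting at OLE entry, not one starting at the first parent dose.

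**Limited consequence.** The analysis is single-arm and descriptive, and SAP Section 11 records that the programme has been discontinued. Protocol Section 1.3.2 says of the parent study: "No dose-limiting toxicities (DLTs) or related serious adverse events (SAEs) were reported". Any omitted death reported as an SAE would therefore be one judged unrelated. All of this lowers the importance without removing the mismatch.

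**Conclusion.** The concern holds. The pairing of time origin and cohort in Section 9.2.1.2 does not give the probability that the section defines. Barring eligibility deviations, deaths by death date and permanent stops by stop date are absent from the first three intervals by construction. Each omitted early event is worth about 1.4 percentage points there, assuming no other dropout. The actual size is unknown and may be nil; the disposition table in SAP Section 7.1 will show how many of the 69 did not enter the OLE, which caps it.

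Three stronger readings are not supported:

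- A reader might infer that all later cumulative values are too low. The second case in step 5 of the working shows that they need not be. They are conditional on reaching the OLE, with bias in either direction.
- A reader might extend the early zero to all TEAEs. Events that neither killed nor ended treatment can appear early, though only in a selected group.
- A reader might infer that early parent-study harm is hidden. The documents report no such counts, and the crude columns may show any such events.

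This should be fixed, but no test or decision rule depends on it.

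**What to change.** In SAP Section 9.2.1.2:

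1. For cumulative rates timed from the first parent dose, use the NEOD001 Safety Population already defined in Section 5, and censor subjects who did not enter the OLE at the end of their parent-study AE follow-up.
2. For the OLE Safety Population, start the clock at the first OLE dose. Alternatively, keep time since first parent dose with delayed entry at the first OLE dose, count only events after it, and label the curve as conditional on reaching the OLE.
3. State whether onset date or outcome date places a fatal or treatment-ending TEAE in an interval.
4. Confirm that Section 9.2.1.1 is the exception to the default population in Section 9.2.

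The cost is SAP wording plus a changed population flag and entry time; Table 6 already requires the combined parent and OLE AE data. The downside is that early rates for fatal and treatment-ending events may look less favourable, and an OLE-clock or delayed-entry curve says nothing about risk before OLE entry.
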